**Figure 2. Overall Study Design**

The proposed doses, schedule(s) and PK time points may be reconsidered and amended during the study based on the emerging safety and PK data. Intermediate doses may be evaluated.

### 3.1.1. Criteria for Dose Escalation

In Part 1 of the study, dose escalation and de-escalation will follow a modified Toxicity Probability Interval (mTPI) method, targeting a DLT rate of 27.5% and an acceptable DLT interval 22.5 to 32.5%. The dose levels to be evaluated in Part 1 of the study are listed in the following table:

**Table 1. Dose Escalation Potential Dose Levels**

| Potential Dose Level | PF-06840003 (mg QD)*  | PF-06840003 (mg BID)  |
|----------------------|---|---|
| Starting Dose        | 125   | N/A   |
| 2                    | 250   | N/A   |
| 3                    | 500   | 250   |
| 4                    | 750   | 500   |
| 5                    | 1000  | 750   |
| 6                    | To be determined  | 1000  |
| 7                    | Escalation to continue to the MTD or desired pharmacological activity | Escalation to continue to MTD or desired pharmacological activity |

\* While a more frequent dosing regimen is initiated for further escalation towards the MTD, the escalation with a QD regimen will be suspended.

The mTPI method relies upon a statistical probability algorithm, calculated using all patients treated in the current dose level to determine one of the following dose-finding decisions: the subsequent dose should be escalated, maintained at the current dose, or de-escalated in the next cohort of 2 to 4 patients, or the trial should be terminated.

As an example, if the total number of patients treated at the current dose level is 4, the following dosing rules are applied:

- 0 DLT -> escalate
- 1 DLT -> remain at the same dose
- 2 DLTs -> de-escalate
- 3-4 DLTs -> de-escalate and consider current dose as intolerable

The general approach to dose-finding, using the mTPI method, involves the following:

- The target cohort size is 2 to 4, depending on the number of potential patients identified at participating sites;
- The next cohort can be enrolled when all patients at the current dose cohort have been evaluated for 28 days of the first treatment cycle, or experience a dose-limiting toxicity (DLT), whichever comes first;
- If a patient withdraws from the study before receiving  $\geq 80\%$  of the planned first-cycle dose for reasons other than investigational product-related toxicity, another patient will be enrolled to replace that patient at the current dose combination;
- In the situation in which the safety of the starting dose does not allow for escalation to the next dose level, a lower dose will be considered.

The dose escalation portion of the study is completed when at least 6 to 12 evaluable patients have been treated at the highest dose associated with DLT rate  $\leq 32.5\%$ .

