**Table 2. Decision Rules**

| Number of Patients having DLT | Number of Patients Treated at a Dose Level |     |     |     |     |     |     |     |      |      |      |
|-------------------------------|--|-----|-----|-----|-----|-----|-----|-----|------|------|------|
|                               | n=2  | n=3 | n=4 | n=5 | n=6 | n=7 | n=8 | n=9 | n=10 | n=11 | n=12 |
| 0                             | E  | E   | E   | E   | E   | E   | E   | E   | E    | E    | E    |
| 1                             | S  | S   | S   | E   | E   | E   | E   | E   | E    | E    | E    |
| 2                             | U  | D   | S   | S   | S   | S   | S   | S   | S    | E    | E    |
| 3                             |  | U   | U   | D   | D   | S   | S   | S   | S    | S    | S    |
| 4                             |  |     | U   | U   | U   | U   | D   | D   | D    | S    | S    |
| 5                             |  |     |     | U   | U   | U   | U   | U   | D    | D    | D    |
| 6                             |  |     |     |     | U   | U   | U   | U   | U    | U    | U    |
| 7                             |  |     |     |     |     | U   | U   | U   | U    | U    | U    |

Actions to be taken:

D = De-escalate the dose; E: Escalate the dose; S: Stay at the dose.

U = Unacceptable toxicity.

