**3.3. MTD Definition**

The estimated MTD is the dose level associated with approximately 27.5% of DLT-evaluable patients experiencing a DLT. The target interval for the DLT rate is (22.5%, 32.5%) Due to the discreteness of the dose levels and in the interest of the safety of the patients, the estimated MTD is the highest tested dose level with DLT rate  $\leq$ 32.5% (see [Table 2](#)).

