### **5.1. Allocation to Treatment**

Dose level allocation will be performed by the sponsor after patients have given their written informed consent and have completed the necessary screening assessments. Registration should occur before any other Day 1 activities are performed and preferably no more than 3 business days before Day 1. The site staff will email a complete Patient Enrollment Form to the designated sponsor study team member. The sponsor will assign a patient enrollment number and this email to the site.

No patient shall receive investigational product until the investigator or designee has received the following information in writing from the sponsor:

- confirmation of the patient's enrollment;
- specification of the dose level for that patient and
- permission to proceed with dosing the patient;

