## **9.2. Statistical Methods and Properties**

### **9.2.1. Statistical Methods for Dose Escalation/De-Escalation**

Part 1, the dose escalation phase of this study, employs an mTPI design to estimate the MTD. The mTPI design employs a simple beta binomial model with a conjugated prior beta (0.5, 0.5). Decision rules are based on calculating the unit probability mass (UPM) of 3 intervals corresponding to underdosing, proper dosing, and overdosing in terms of dose limiting toxicity. A proper dosing interval is centered at the target toxicity rate (pT) of 27.5% with 5% uncertainty ( $0.225 < pT < 0.325$ ). The under dosing interval is (0, 0.225), and the overdosing interval is (0.325, 1). The 3 dosing intervals are associated with 3 different dose escalation decisions. The underdosing interval corresponds to a dose escalation I, overdosing corresponds to a dose de-escalation, and proper dosing corresponds to staying at the same current dose. Given an interval and a probability distribution, the UPM of that interval is defined as the probability of the interval divided by the length of the interval. The mTPI design calculates the UPMs for the 3 dosing intervals, and the one with the largest UPM implies the corresponding dose finding decision. That decision provides the dose level to be used for future patients. For example, if the underdosing interval has the largest UPM, decision E (to escalate) will be executed, and the next cohort of patients will be treated at the next higher dose level. Under the mTPI design, a trial is terminated when either the lowest dose is above the MTD or a pre-specified maximum sample size is reached. Doses with an incidence of DLT >33% (eg, 4 out of 10) will not be declared as MTD even though it is allowed by the mTPI method.

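### For 2 DLTs in 4 patients the worked dosing rule says de-escalate, while the decision table and the stated mTPI algorithm say stay

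*Protocol*

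**What the plan says.** Protocol 3.1.1 introduces a worked example of the mTPI method: "if the total number of patients treated at the current dose level is 4, the following dosing rules are applied". For 2 DLTs the listed action is "2 DLTs -> de-escalate". SAP 4.2 repeats the list.

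Protocol Table 2 and SAP Table 1 give the decision for every count at n = 2 to 12. In both, the row for 2 DLTs begins U, D, S for n = 2, 3, 4. The key reads "D = De-escalate the dose; E: Escalate the dose; S: Stay at the dose", so the entry for 2 DLTs in 4 patients is stay.

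Protocol 9.2.1 and SAP 8.1 state the algorithm behind the table: a beta-binomial model with a Beta(0.5, 0.5) prior; underdosing, proper-dosing and overdosing intervals (0, 0.225), (0.225, 0.325) and (0.325, 1); and, for the unit probability mass (UPM) of each interval, "the one with the largest UPM implies the corresponding dose finding decision".

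**The concern.** The worked list and the table agree at 0, 1, 3 and 4 DLTs in 4 patients and conflict only at 2. The conflict is in both documents, so neither can be used to correct the other.

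Under Protocol 5.1, "Dose level allocation will be performed by the sponsor". Whoever does this would hold two written instructions for the same data at a routine size: 4 lies inside the target cohort size of 2 to 4, and it is also reached by two cohorts of 2. One instruction moves the next 2 to 4 patients down a level. The other treats them at a dose where half of the patients so far had a DLT. The choice changes the escalation path and patient exposure, and it can influence which dose becomes the MTD.

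**Working it through.** **Inputs.** Prior Beta(0.5, 0.5), cut-points 0.225 and 0.325, and the largest-UPM rule, all from Protocol 9.2.1 and SAP 8.1. Data: x = 2 DLTs, n = 4.

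**Formula.** The posterior is Beta(0.5 + x, 0.5 + n − x). UPM is the posterior probability of an interval divided by its length.

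**Result at 2/4.** The posterior is Beta(2.5, 2.5).

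| Interval | Probability | Length | UPM | Decision if largest |
|---|---|---|---|---|
| Under | 0.1004 | 0.225 | 0.446 | Escalate |
| Proper | 0.1203 | 0.100 | 1.203 | Stay |
| Over | 0.7792 | 0.675 | 1.154 | De-escalate |

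The proper-dosing interval has the largest UPM, so the stated method gives stay.

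**Rest of the n = 4 column.**

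| DLTs | UPM under / proper / over | Algorithm | Table | Worked rule |
|---|---|---|---|---|
| 0 | 3.820 / 0.734 / 0.099 | Escalate | E | Escalate |
| 1 | 1.809 / 1.906 / 0.596 | Stay | S | Stay |
| 2 | 0.446 / 1.203 / 1.154 | Stay | S | **De-escalate** |
| 3 | 0.051 / 0.279 / 1.423 | De-escalate | U | De-escalate, intolerable |
| 4 | 0.002 / 0.016 / 1.479 | De-escalate | U | De-escalate, intolerable |

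**Whole table.** Counting a U as agreeing when the overdosing UPM is largest, 69 of the 73 filled cells match the stated rule. The documents give no cut-off for U. Assuming U when the posterior probability of a DLT rate above 27.5% exceeds 0.95, the same four cells are the only mismatches. All four are printed D where the rule gives stay:

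| Cell | Observed rate | UPM under / proper / over |
|---|---|---|
| 4/9 | 44% | 0.291 / 1.521 / 1.159 |
| 4/10 | 40% | 0.435 / 1.991 / 1.042 |
| 5/11 | 45% | 0.186 / 1.359 / 1.218 |
| 5/12 | 42% | 0.281 / 1.801 / 1.121 |

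**How often 2/4 is met.** With p the true DLT rate, take one pass through a dose level, continuing only while Table 2 prints S.

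- Cohorts of 4: 6p²(1−p)². At p = 0.275, 6 × 0.0756 × 0.5256 = 0.239.
- Cohorts of 2 (1/2, printed S, then 1/2): [2p(1−p)]². At p = 0.275, 0.39875² = 0.159.
- Cohorts of 3: never at n = 4, so 0.
- Sizes 2, 3 and 4 equally likely (an assumption): one third of the first figure plus one ninth of the second. At p = 0.275, 0.0795 + 0.0177 = 0.097.

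| True rate | Cohorts of 4 | Cohorts of 2 | Cohorts of 3 | Equal mix |
|---|---|---|---|---|
| 5% | 1.4% | 0.9% | 0% | 0.6% |
| 10% | 4.9% | 3.2% | 0% | 2.0% |
| 27.5% | 24% | 16% | 0% | 10% |
| 40% | 35% | 23% | 0% | 14% |

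**If stay is followed.** The chance of at least one more DLT in a next cohort of size s is 1 − (1−p)^s. For s = 2, 3, 4 this is 47%, 62% and 72% at p = 0.275, and 64%, 78% and 87% at p = 0.40.

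**Link to the MTD.** Under Protocol 3.3, "the estimated MTD is the highest tested dose level with DLT rate" at or below 32.5%. From 2/4, two further patients without a DLT give 2/6 = 33.3%, which is too high. Three give 2/7 = 28.6%, the first eligible ratio.

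**The case against.** The strongest reply is that the algorithm does not settle what the sponsor intended. The margin at 2/4 is about 4% (1.203 against 1.154). A uniform Beta(1, 1) prior would just tip it to de-escalate (1.1886 over, 1.1876 proper). The printed table is itself stricter than the algorithm in four cells, so a cautious rule at a 50% observed rate could be deliberate. This stands as a caution about intent. However, Beta(1, 1) is not the stated prior and fits the printed table worse (8 mismatches against 4, using the 0.95 cut-off for U). The worked line is offered as an application of mTPI, and neither document describes it as an override. The one departure stated in Protocol 9.2.1 is "Doses with an incidence of DLT >33% (eg, 4 out of 10) will not be declared as MTD even though it is allowed" by the method. That limits which dose may be declared the MTD; it does not set the next cohort's dose.

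Safeguards also limit the harm: the 32.5% ceiling on the MTD, central allocation, and the ongoing sponsor–investigator discussions in Protocol 9.8. They make an unnoticed error less likely, but none says which instruction wins.

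The frequency depends on the true DLT rate, which the documents do not predict. At 5% to 10%, plausible at early dose levels, 2/4 is uncommon. The chance of a further DLT at p = 27.5% is also not evidence of harm in itself, because that is the target rate and any cohort treated there carries the same risk.

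The four stricter cells are a minor matter. Each gives the user one clear answer, and each errs towards caution.

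**Conclusion.** The point holds. Each document gives opposite next-cohort instructions for 2 DLTs in 4 patients. The table follows the stated algorithm and the worked rule does not, so the worked rule is wrong as written. This conclusion rests only on the prior, cut-points and decision rule printed in the documents.

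The conflict is reachable at the target DLT rate: 24% per dose level with cohorts of 4, 16% with cohorts of 2, and 10% under the assumed equal mix of sizes. It bears on exposure and the escalation path. It can influence the MTD but does not fix it, since at least three further DLT-free patients would be needed before such a dose qualified. It should be corrected before any cohort decision relies on it. The four cells at 4/9, 4/10, 5/11 and 5/12 are a secondary inconsistency, possibly intended.

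**What to change.** Make the worked rule and the table cell agree in both documents, in one of two ways:

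- change the 2-DLT line in Protocol 3.1.1 and SAP 4.2 to staying at the same dose, which is what the algorithm gives; or
- change the 2/4 cell in Protocol Table 2 and SAP Table 1 to D, and state in Protocol 9.2.1 and SAP 8.1 that it is a safety override of the UPM rule.

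Which action is clinically right at a 50% observed DLT rate is for the sponsor and investigators.

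In the same edit, either mark 4/9, 4/10, 5/11 and 5/12 as deliberate overrides or change them to S. Marking them keeps the more cautious decision.

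The cost is a text and table correction in the protocol and SAP, with no added patients or procedures.

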**Table 2. Decision Rules**

| Number of Patients having DLT | Number of Patients Treated at a Dose Level |     |     |     |     |     |     |     |      |      |      |
|-------------------------------|--|-----|-----|-----|-----|-----|-----|-----|------|------|------|
|                               | n=2  | n=3 | n=4 | n=5 | n=6 | n=7 | n=8 | n=9 | n=10 | n=11 | n=12 |
| 0                             | E  | E   | E   | E   | E   | E   | E   | E   | E    | E    | E    |
| 1                             | S  | S   | S   | E   | E   | E   | E   | E   | E    | E    | E    |
| 2                             | U  | D   | S   | S   | S   | S   | S   | S   | S    | E    | E    |
| 3                             |  | U   | U   | D   | D   | S   | S   | S   | S    | S    | S    |
| 4                             |  |     | U   | U   | U   | U   | D   | D   | D    | S    | S    |
| 5                             |  |     |     | U   | U   | U   | U   | U   | D    | D    | D    |
| 6                             |  |     |     |     | U   | U   | U   | U   | U    | U    | U    |
| 7                             |  |     |     |     |     | U   | U   | U   | U    | U    | U    |

Actions to be taken:

D = De-escalate the dose; E: Escalate the dose; S: Stay at the dose.

U = Unacceptable toxicity.

### 3.2. DLT Definition

Severity of AEs will be graded according to CTCAE version 4.03. For the purpose of dose escalation, any of the following adverse events occurring in the first cycle of treatment (28 days) will be classified as DLTs, unless there is a clear alternative explanation (eg, related to underlying disease/progression, change in concurrent medication or co-morbid event):

#### Hematologic:

- Grade 4 neutropenia lasting  $\geq 5$  days;
- Febrile neutropenia [defined as absolute neutrophils count (ANC)  $< 1,000/\text{mm}^3$  with a single temperature of  $> 38.3^\circ\text{C}$  ( $101^\circ\text{F}$ ) or a sustained temperature of  $\geq 38^\circ\text{C}$  ( $100.4^\circ\text{F}$ ) for more than one hour];
- Grade  $\geq 3$  neutropenia with infection;
- Grade  $\geq 3$  thrombocytopenia with bleeding;

- Grade 4 thrombocytopenia.

**Non-hematologic:**

- Any toxicity attributable to PF-06840003 that results in administration of less than 80% of the planned doses during Cycle 1.
- Grade 4 non hematologic AE.
- Grade 3 AE lasting >7 days despite optimal supportive care.
- Grade 3 CNS AE regardless of duration. CNS AEs are those events listed within the nervous system disorders category in the NCI CTCAE version 4.03.
- Grade 3 QTc prolongation (QTc >500 msec) will be considered a DLT only if persisting after correction of any reversible causes.
- Concurrent aspartate aminotransferase (AST) or alanine aminotransferase (ALT) >3 x upper limit of normal (ULN) and total bilirubin >2 x ULN.

The following AEs will not be considered as DLTs:

- Isolated Grade 3 or 4 laboratory abnormalities that are not associated with clinical sequelae or are corrected to Grade  $\leq$ 1 with supplementation/appropriate management within 72 hours of their onset.

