**3.4. Late Onset Toxicity and Toxicities Observed in the Expansion Phase**

Adverse events that meet the same grading criteria as the DLT criteria listed above occurring after the DLT observation period will lead Pfizer to immediately schedule a meeting with the investigators to review the details of the potential late onset toxicity and determine if the enrollment has to be held for this dose level or if a dose reduction should be implemented for all ongoing patients. Late onset toxicities meeting the definition of a DLT will be used in the evaluation of the MTD.

In addition, adverse events that meet the same grading criteria as the DLT criteria listed above occurring in the expansion phase (Part 2) will prompt Pfizer to immediately schedule a meeting with the investigators to review the details of the toxicity and determine the necessary action to be implemented for all patients.

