### **4.1. Inclusion Criteria**

Patient eligibility should be reviewed and documented by an appropriate member of the investigator's study team before patients are included in the study.

Patients must meet all of the following inclusion criteria to be eligible for enrollment into the study:

1. Pathologically documented and definitively diagnosed recurrent WHO Grade IV GBM.
2. Pathologically documented and definitively diagnosed recurrent WHO Grade III anaplastic gliomas (including anaplastic astrocytoma, anaplastic oligodendroglioma, anaplastic oligoastrocytoma and mixed gliomas) – Part 1 only.
3. Access to archived formalin fixed paraffin embedded material from the initial diagnosis or subsequent relapse of Grade IV GBM or Grade III anaplastic glioma that is of diagnostic quality and representative of their diagnosed malignancy available for submission to the sponsor. If archival tissue is not available, the patient must consent to surgical intervention to acquire tumor tissue at screening.
4. For patients with Grade IV GBM, recurrent disease (confirmed by MRI and evaluable by Macdonald criteria) at the time of first or second recurrence or progression following prior definitive therapy(s) such as surgery with adjuvant radiation therapy and/or chemotherapy. For patients with Grade III anaplastic glioma, recurrent disease (confirmed by MRI and evaluable by Macdonald criteria) at the time of at least a first recurrence but no more than a fourth recurrence or progression following prior definitive therapy(s).
5. Must have recovered to Grade 0 or 1 or pre-treatment baseline from clinically significant toxic effects of prior therapy (including but not limited to exceptions of alopecia, laboratory values listed per inclusion criteria, and lymphopenia which is common after therapy with temozolomide).

6. Must have stable dosing of corticosteroid treatment for at least 7 days prior to registration and are neurologically stable.
7. Must have recovered from the acute effects of radiation therapy or surgery or systemic treatment prior to study entry.
8. Age  $\geq 18$  years.
9. Karnofsky performance score  $\geq 70\%$ .
10. Have received no more than two prior lines of therapy.
11. Adequate Hematologic Function, including:
  - a. Absolute Neutrophil Count (ANC)  $\geq 1,500/\text{mm}^3$  or  $\geq 1.5 \times 10^9/\text{L}$ ;
  - b. Platelets  $\geq 100,000/\text{mm}^3$  or  $\geq 100 \times 10^9/\text{L}$ ;
  - c. Hemoglobin  $\geq 9$  g/dL.

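### Section 3.2 lists uncomplicated Grade 4 thrombocytopenia and prolonged Grade 4 neutropenia as DLTs, but its laboratory exclusion, read literally, removes both, and no text says which line prevails

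*Protocol*

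**What the plan says.** The hematologic list in Protocol Section 3.2 includes "Grade 4 thrombocytopenia" with no bleeding condition, and "Grade 4 neutropenia lasting" 5 days or more with no fever or infection condition. The complicated forms have separate lines: febrile neutropenia, Grade 3 or higher neutropenia with infection, and Grade 3 or higher thrombocytopenia with bleeding.

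At the end of the non-hematologic list a new lead-in appears: "The following AEs will not be considered as DLTs". One item follows: "Isolated Grade 3 or 4 laboratory abnormalities that are not associated with clinical sequelae or are corrected to Grade" 1 or lower, with supplementation or other management, within 72 hours of onset. The two conditions are joined by *or*, so absence of sequelae is enough on its own. Table 4 of the protocol lists platelets and absolute neutrophils among the laboratory assessments.

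The only exception in the opening sentence of Section 3.2 is a clear alternative explanation for the event. SAP Sections 6.1 and 8.2.4.1 refer back to the protocol for the DLT definition and add no precedence rule.

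**The concern.** An uncomplicated Grade 4 platelet count, or a Grade 4 neutrophil count lasting 5 days or more without fever or infection, satisfies both a DLT line and the exclusion. Whoever classifies the event must choose between them without guidance.

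The error can go only one way. Applying the exclusion literally can lower the DLT count but never raise it, so it favours escalation. With target cohorts of 2 to 4 patients, a single classification can set the dose decision. The ambiguity also reaches past Cycle 1, because Section 3.4 states: "Late onset toxicities meeting the definition of a DLT will be used in the evaluation of the MTD".

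**Working it through.** **1. The two rules side by side**

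| Event | DLT list | Exclusion, read literally |
|---|---|---|
| Grade 4 thrombocytopenia, no bleeding | DLT | Not a DLT (no sequelae) |
| Grade 4 neutropenia for 5 days or more, no fever or infection | DLT | Not a DLT (no sequelae) |

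The neutropenia line is reached only through the no-sequelae condition, because an event lasting at least 5 days cannot have been corrected within 72 hours. If *or* had been *and*, that line could never be excluded, and the platelet line could be excluded only after correction within 72 hours.

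**2. Effect on the dose decision**

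Inputs: Protocol Section 9.2.1 gives a Beta(0.5, 0.5) prior and the intervals (0, 0.225), (0.225, 0.325) and (0.325, 1). With x DLTs in n patients, the posterior is Beta(0.5 + x, 0.5 + n − x). The unit probability mass (UPM) of an interval is its posterior probability divided by its length (0.225, 0.1 or 0.675). The largest UPM gives the decision, coded as in Table 2: "D = De-escalate the dose; E: Escalate the dose; S: Stay at the dose".

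| DLTs / n | UPM under | UPM proper | UPM over | Decision | Table 2 |
|---|---|---|---|---|---|
| 0/2 | 3.190 | 1.007 | 0.269 | E | E |
| 1/2 | 0.749 | 1.134 | 1.064 | S | S |
| 0/3 | 3.569 | 0.880 | 0.161 | E | E |
| 1/3 | 1.298 | 1.642 | 0.806 | S | S |
| 2/3 | 0.199 | 0.626 | 1.322 | D | D |
| 0/4 | 3.820 | 0.734 | 0.099 | E | E |
| 1/4 | 1.809 | 1.905 | 0.596 | S | S |

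All seven cells reproduce Table 2. If the event is the only DLT and is not counted, Stay becomes Escalate at n = 2, 3 and 4. If a cohort of 3 has one other DLT, De-escalate (2/3) becomes Stay (1/3).

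**3. What the dose-intensity line would still catch**

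Section 3.2 also lists as a DLT: "Any toxicity attributable to PF-06840003 that results in administration of less than 80% of the planned doses during Cycle 1". For a 28-day cycle:

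- QD: 5 missed doses leave 23/28 = 82.1% (not caught); 6 missed leave 22/28 = 78.6% (caught).
- BID: 11 missed leave 45/56 = 80.4% (not caught); 12 missed leave 44/56 = 78.6% (caught).
- First found on Day 24: Days 24 to 28 hold 5 QD or 10 BID doses. Missing all of them leaves 23/28 or 46/56, both 82.1% (not caught).

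Table 3 withholds dosing for Grade 4 hematologic toxicity until Grade 1 or baseline, so an event found early in the cycle would often cost 6 or more QD doses. Detection only on Day 24 or later should be uncommon. Scheduled Cycle 1 hematology falls on Days 1, 4, 8, 15 and 22 (±1 day for the last three), so later detection needs an unscheduled test or an early draw for Cycle 2 Day 1. Neutropenia starting on Day 25 has only 4 days (25 to 28) left in the window, so it cannot complete 5 days within it.

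**The case against.** The strongest reply is that the intended meaning can be recovered from the text. Grade 4 thrombocytopenia with bleeding is already covered by the Grade 3-or-higher line, so the separate Grade 4 line exists for cases without bleeding; an exclusion removing those would leave it almost nothing to do. The 5-day neutropenia threshold loses most of its purpose in the same way. The exclusion is printed under the non-hematologic heading, where it has a natural job: keeping trivial chemistry values out of the generic Grade 3 and Grade 4 lines. The mention of supplementation fits electrolytes. Most of this stands, and it makes the intended reading fairly clear. It does not make it stated: the exclusion has its own unrestricted lead-in, and no text limits it.

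A second reply is that other rules catch the event. The dose-intensity line does so often, but only partly. It needs attribution to the drug, whereas the main rule needs only the absence of a clear alternative explanation. It covers Cycle 1 only. It is also itself a listed DLT, so relying on it assumes that a listed line beats the exclusion, which is the open question. If the heading confines the exclusion to non-hematologic events, it should confine the dose-intensity line too, and that line could then not catch a cytopenia.

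Section 3.4 does call an immediate meeting for late events that meet the DLT grading criteria, probably whatever the exclusion means, and Section 9.8 provides for ongoing review of adverse events at each dose level. Both protect patients. Neither says whether the event enters the DLT count.

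The Table 2 shifts are what dropping any single DLT would do; they show sensitivity and do not measure how often this ambiguity would matter. That is correct.

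**Conclusion.** Section 3.2 contains two lines that conflict on their wording, and neither document settles the order. The listed hematologic DLTs are probably meant to count. If the exclusion were applied literally instead, one uncomplicated event as the only DLT would turn Stay into Escalate with 2, 3 or 4 patients. That result rests on Table 2 alone, with no assumed rates.

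A reader might infer three stronger things that the documents do not support:

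- **That the plan in fact drops these cytopenias from the DLT count.** Placement and the near-redundancy of the Grade 4 platelet line point the other way.
- **That the chance of escalating past a toxic dose rises by some stated amount.** The documents give no rate for these events. Section 1.5.2 names the hematopoietic system as a target in dogs, but the blood-count change it describes is reduced red cell mass, called non-adverse; it reports no fall in platelets or neutrophils. Any probability would rest on an invented share.
- **That such events would go unnoticed.** Dose-holding under Table 3, the scheduled blood counts and the sponsor–investigator reviews make that unlikely. What is unsettled is how the event is counted.

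This is a minor but worthwhile safety correction to the definition that drives the Part 1 dose decisions.

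**What to change.** In the exclusion, insert after the word *abnormalities*: *, other than the hematologic DLTs and the concurrent AST/ALT-plus-bilirubin criterion listed above,* and leave the rest unchanged. The liver clause is precautionary: a concurrent rise is arguably not isolated, but the same question could be raised.

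This wording keeps the exemption for every other laboratory value, including unlisted hematologic ones such as the "lymphopenia which is common after therapy with temozolomide" mentioned in Section 4.1. Changing *or* to *and* instead would narrow the exemption for all laboratory values and is not needed to protect the two listed events.

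The cost is one protocol clause, with no new data and no SAP change, since the SAP refers to the protocol definition. The downside is that slightly more events count as DLTs than under the literal exclusion, so escalation may be slightly slower.
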